17.3 Subject Disposition

The number and percentage of subjects in each of the analysis populations and number and percentage of subjects who discontinued the study prematurely will be summarized by treatment and overall. The reasons for early study termination will also be presented. Details of study disposition and inclusion/exclusion criteria for all subjects will be listed.

17.4 Demographics and Baseline Characteristics

Demographic and baseline characteristics including age, gender, race and relevant baseline medical conditions will be summarized by treatment and overall. Descriptive statistics will be presented, but no statistical testing will be performed. Subject demographic and baseline characteristics and medical conditions will be listed.

17.5 Efficacy Analysis

Efficacy data from the Randomized Treatment phase will be evaluated by inspection, using student T-test, Cochran Mantel Hansel, or Kruskal-Wallis tests as appropriate; without conservation of alpha at 0.05. An interim analysis will be completed after approximately 50% of the study subjects (n=30) have been accrued.

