- 3) Place a human fibroblast growth factor-2 (FGF-2) soaked pledget of bioabsorbable gelatin sponge larger than the tympanic membrane so the tympanic membrane is completely covered.
- 4) Secure the pledget in place with several drops of fibrin glue.
- 5) After the effects of the topical anesthetic have worn off, if any, the patient is released with the following instructions:
 - a) Avoid violently sniffling or blowing the nose
 - b) Sneeze and cough naturally through the mouth without occluding the mouth with the hand.
 - c) Use cotton balls covered with petroleum jelly on the outer surface when washing the hair and bathing. This is needed to help keep water out of the ear.
 - d) Avoid using a hearing aid in the treated ear.
 - e) Avoid flying, using elevators in tall buildings, and other situations involving substantial changes in air pressure.
 - f) Avoid swimming.

DISCONTINUATION FROM TREATMENT:

Reasons for permanent discontinuation include the following:

If the first treatment does not result in complete closure, subsequent treatments will not be administered if any ear complications occur in the treated ear, including but not limited to infection, moderate to severe pain, moderate to severe irritation, or clinically significant sensorineural hearing loss. All subjects will complete all safety follow up visits.

PRIMARY ENDPOINT:

The tympanic membrane and surrounding structures will be examined every 21-days (+7 days) for up to three visits. Adverse events will be recorded at all visits. Routine laboratory tests will be performed at the screening visit and at the final study visit. Vital signs will be assessed at each study visit and changes in clinical examination findings will be noted.

SECONDARY ENDPOINTS:

- Tympanic membrane perforation closure determined by otoscopic exam and photographic documentation
- Pure-tone and speech discrimination scores as measured by pre- and post-treatment audiograms
- Mobility of the tympanic membrane as measured by tympanometry
- Salvage rate of FGF-2 in patients who fail placebo

STATISTICAL ANALYSIS:

The target enrollment of 75 subjects will provide sufficient power while also accounting for potential retention issues. The primary endpoint is to confirm the efficacy of

FGF-2 in subject with TMR by testing the hypothesis that the rate of subject with complete closure of the TMR will be superior to that placebo.

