The sample size is calculated in 3:1 ratio to FGF-2 treatment group or placebo to provide more than 90% power to detect a clinical significant difference at a two-sided significance level of 0.05 using a Fisher's exact test. To allow for 5% dropouts, 45 patients of FGF-2 treatment group and 15 patients of placebo are required.

Data after discontinuations for any reason will not be imputed through the final schedule visit. This subject will be considered as not-improvement.

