17.2 Subject Populations

The following populations will be used for the analysis of data for this study:

Per Protocol (PP) Population: All subjects who have been selected and received the specified drug at Visit 1 and do not have any important protocol deviations will be included in the PP population. The PP population will be the primary population for the analysis of efficacy.

Safety Population: All subjects who received the drug will be included in the safety population. The safety population will be the primary population for analysis of demographic, accountability, and safety measures.

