17.6 Secondary Efficacy Analysis

Secondary analysis of categorical data will be performed using Fisher's exact test for paired samples.

18. Safety Analysis

Safety will be assessed by evaluation of adverse events and clinical laboratory results and derived as data sets and frequency methods.

An independent Data and Safety Monitoring Board (DSMB) will follow the DSMB charter for this study. The DSMB Charter is commensurate with the level of risk of the study to its participants, complexity of the protocol, and ensure compliance with the principles and process of informed consent as well as privacy related regulations (e.g., HIPAA); and to monitor safety by recording (un-)expected adverse events (AEs) and their severity and attribution. The DSMB Charter includes a plan for periodic reviews of primary results and summary data as well as assessment of completeness and quality of collected data. All unexpected and/or serious adverse events as well as premature study withdrawals will be brought to the attention of the DSMB as early as possible in order for the DSMB to make judgments about participant safety, study modifications, and/or continuation. Not beyond the commencement of the proposed subsequent dose escalated cohorts, the DSMB will review study status to determine study progression. These will be based upon discussions between the research team and DSMB, and the decision of the board; no set stopping or escalating rules will be employed. The DSMB membership list is as follows:

[name], PhD - Chair and Research Monitor
MGH, Dana Farber/Harvard Cancer Center
Division of Hematology Oncology
[name]
[name]
Phone: [[name]]([contact])
Fax: [[name]]([contact])
Email: [contact]

[name], - Member
University of Minnesota
Department of Pediatrics
[name]
[name]
[name]
Phone: [[name]]([contact])
Fax: [[name]]([contact])
Email: [contact]

[name], Member (Statistician)
Director, Cooperative Studies Program Coordinating Center
Hines VA Hospital, CSPCC (151K)
[name],
[name]
Phone: [[contact]]([contact])
Fax: [[contact]]([contact])
[contact]

19. Research Monitor

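### Section 17.5 does not carry forward the two-sided 0.05 Fisher's exact test on which the synopsis sizes the trial, and it adds an n=30 interim analysis with no stated purpose or boundary

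*Combined protocol and SAP*

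**What the plan says.** The synopsis, under statistical analysis, describes the primary aim as "testing the hypothesis that the rate of subject with complete closure of the TMR will be superior to that placebo". It sizes the trial for more than 90% power "at a two-sided significance level of 0.05 using a Fisher's exact test", with 45 FGF-2 and 15 placebo subjects.

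Section 17.5 says that Randomized Treatment phase efficacy data "will be evaluated by inspection, using student T-test, Cochran Mantel Hansel, or Kruskal-Wallis tests as appropriate; without conservation of alpha at 0.05". It does not mention Fisher's test. It continues: "An interim analysis will be completed after approximately 50% of the study subjects (n=30) have been accrued". It gives no endpoint, decision, boundary or responsible party for that look.

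In the analysis sections, Fisher's test appears only in section 17.6: "Secondary analysis of categorical data will be performed using Fisher's exact test for paired samples".

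Section 18 says of the monitoring board: "The DSMB Charter includes a plan for periodic reviews of primary results and summary data". It adds that "no set stopping or escalating rules will be employed", in text about commencing dose-escalated cohorts. The charter is not part of these documents.

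**The concern.** A plan that sizes on one test and one error rate should analyse with the same test and rate, or explain the change. Here the sizing test is absent from the section that should name the primary analysis. That section offers three other tests, refers to inspection of the data, and sets aside control of alpha at 0.05. If the listed tests gave different answers on the closure data, nothing in section 17.5 would say which one decides the superiority claim. The interim raises a second question. If success could be declared at n=30 as well as at the end, each at 0.05, the overall false-positive rate would no longer be the 0.05 used for sizing.

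**Working it through.** **Inputs.** Fisher at two-sided 0.05, and 45:15 (synopsis). Interim at n=30 (section 17.5). Target of 60 (section 17.1) or 75 (synopsis). Sets of four with three FGF-2 and one placebo (section 10.2). Seven full sets give 21:7, so n=30 is 23:7 or 22:8. Eighteen full sets give 54:18, so n=75 is 56:19 or 57:18. All results are exact binomial enumerations, rejecting when p ≤ 0.05.

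**The plan's own figure.** The power above 90% cannot be reproduced, because no design closure rates are stated. Under assumed rates, Fisher power at 45:15 is 92.7% for 80% vs 30% and 78.0% for 81% vs 41% (the animal rates in section 3.1). It is about 100% for 98.1% vs 10% (the same-method human rates in section 3.2). The stated figure is therefore not shown to be wrong.

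**Step 1: can the test change the answer?** Write i for closures among n₁ FGF-2 subjects, m for total closures and N for all subjects. One-stratum CMH without continuity correction is

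χ² = (i − n₁m/N)² / [n₁n₂m(N−m) / (N²(N−1))], on 1 df.

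Take 36/45 (80%) vs 8/15 (53%), so m = 44. The expected count is 45×44/60 = 33. The variance is 45×15×44×16/(3600×59) = 2.237. Then χ² = 3²/2.237 = 4.02 and p = 0.045. Fisher gives p = 0.088. With a continuity correction the same table gives 2.5²/2.237 = 2.79 and p = 0.095.

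Over all possible tables:

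| Split | Tables | Uncorrected CMH only | Fisher only (vs uncorrected) | Corrected CMH only | Fisher only (vs corrected) |
|---|---|---|---|---|---|
| 45:15 | 46×16 = 736 | 28 (14 favour FGF-2) | 0 | 0 | 26 |
| 56:19 | 57×20 = 1140 | 36 (18 favour FGF-2) | 0 | 0 | 32 |

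The direction of the disagreement therefore depends on the form of CMH, which the plan does not give. Section 26 describes two sites; a site-stratified CMH was not modelled.

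**Step 2: how likely is a disagreement?** Uncorrected CMH rejects whenever Fisher does, so the probability of disagreement is the difference in power. At 45:15:

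| Closure rates | CMH power | Fisher power | Difference |
|---|---|---|---|
| 70% vs 30% (assumed) | 79.9% | 72.8% | 7.1 points |
| 75% vs 30% (assumed) | 89.6% | 84.3% | 5.3 points |
| 81% vs 41% (section 3.1) | 84.6% | 78.0% | 6.6 points |
| 98.1% vs 10% (section 3.2) | about 100% | about 100% | about 10⁻⁹ |

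With equal closure rates of 5-50% in both arms, the probability of disagreement is 1.2-2.7%.

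**Step 3: single-look type I error.** The maxima for Fisher / uncorrected CMH are 3.51% / 5.45% at 45:15, 3.42% / 4.97% at 56:19 and 3.56% / 4.91% at 57:18. At 75 subjects, uncorrected CMH alone stays below 5%.

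**Step 4: two looks.** This assumes that success may be claimed at 0.05 at either look and that 30 complete outcomes exist at the first. Ranges cover interim splits 23:7 and 22:8.

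| Final split | CMH maximum | CMH at 10% null closure | CMH at 5% null closure | Fisher maximum |
|---|---|---|---|---|
| 45:15 | 7.9-8.3% | 5.2-5.3% | 3.6-3.9% | 5.0-6.0% |
| 56:19 | 8.1-8.6% | 5.8-6.0% | 4.1-4.4% | 5.1-6.2% |
| 57:18 | 7.9-8.5% | 5.3-5.5% | 3.7-4.0% | 5.1-6.0% |

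CMH is uncorrected and one-stratum throughout. At 10% null closure, the control rate in the human study cited in section 3.2, the excess is small. At 5% there is none.

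**The case against.** The other side has several fair points.

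- **Choice by data type.** Section 17.5 covers all Part A efficacy data, audiometry included, so the wording that lets the test suit the data is ordinary, and CMH would be the natural option for closure. The menu also gives little freedom on a binary outcome: at 45:15 and 56:19 the pooled t-test and uncorrected CMH reach the same decision on every table. This stands. CMH is still not the sizing test, and its strata and correction are not given.
- **Alpha.** A reader might infer that the plan abandons the 0.05 level altogether. The clause can equally mean that several Phase 2 endpoints are not adjusted for multiplicity. The documents do not settle which, so only the ambiguity can be charged.
- **Fisher is in the plan.** It is named in the synopsis, and section 17.6 assigns it to secondary categorical data, while the synopsis lists closure among the secondary endpoints. A reader should therefore not conclude that no test exists. The defect is inconsistency: sections 4, 4.1 and 5.1 make closure primary, and a paired test does not fit two independent arms.
- **The interim.** A reader might infer that the n=30 look inflates type I error. The documents do not support that. The look may be for safety or futility only, and the charter may define it. It is also triggered by accrual, whereas Part A closure is assessed up to Day 64, so 30 complete outcomes may not exist. Nor may one infer from the absence of stopping rules in section 18 that an efficacy claim is excluded, because that sentence concerns dose escalation and is not linked to this look.
- **Large effects.** At the human rates in section 3.2, either test would succeed. That is true, but the plan does not name those rates as its design assumption.

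**Conclusion.** Section 17.5 and the synopsis conflict on the primary test and leave its alpha unclear. This is a contradiction in the text, not merely a missing detail, and it should be corrected. Its numerical weight is modest. The choice of test matters for borderline results: about 5-7% probability of disagreement at 45:15 under the moderate rates assumed, for uncorrected one-stratum CMH, and essentially zero at 98.1% vs 10%.

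The figures do not show that CMH is generally the more lenient choice, since the direction reverses with a continuity correction. The type I error figures of 7.9-8.6% (uncorrected CMH) and 5.0-6.2% (Fisher) are maxima over the null closure rate. They apply only if efficacy may be claimed at 0.05 at both looks with 30 complete outcomes at the first. A safety-only or futility-only look causes no inflation. The undefined role of the interim and the paired-samples wording in section 17.6 are real drafting faults of lesser weight.

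**What to change.** 1. In section 17.5, name the two-sided Fisher's exact test at 0.05, comparing FGF-2 with placebo on complete closure at the end of the Randomized Treatment phase, as the single primary test. For that test, remove the reference to inspection and the clause on alpha. If the clause meant that secondary endpoints are not adjusted for multiplicity, say so separately. Keep the t-test and Kruskal-Wallis for continuous outcomes.
2. State that the n=30 interim makes no efficacy claim. If a claim is wanted, give a boundary and align the charter with it. For example, Fisher p < 0.001 at the interim and 0.05 at the end keeps type I error at or below 3.6% for all the splits above. Do not rely on the dose-escalation sentence in section 18 for this.
3. Reconcile the closure definition in section 13.2, which requires durability at a test-of-cure Visit 5, with section 14.5, which limits Visit 5 to crossed-over subjects. The primary endpoint must be assessable in all randomized subjects.
4. In section 17.6, delete the paired-samples qualifier for between-arm comparisons.

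The cost is wording, plus the charter if a boundary is chosen. Fisher gives up about 5-7 points of power against uncorrected CMH at 45:15 for moderate effects. At 56:19 the loss is 4.5 points for 70% vs 30% (88.1% vs 83.6%) and 3.0 points for 81% vs 41% (90.7% vs 87.7%). Against the single final Fisher test on which the trial was sized, an interim without an efficacy claim costs no power.

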Up to 50 percent of TMPs are refractory to spontaneous healing and require surgical repair depending upon the etiology of the perforation. There is a higher incidence of middle ear contamination with resultant increased incidence of acute and chronic otitis media and chronic middle ear scarring or tympanosclerosis with a resultant conductive hearing loss. Profound sensorineural hearing loss, balance dysfunction, meningitis or brain abscess are rare but serious complications, which may occur from middle ear infection. Long-term effects may include speech and language acquisition delay in children as well.

Some subjects undergo multiple attempts at surgical repair without attaining closure of the tympanic membrane. The underlying cause of the perforation may be an important factor in the inability of the body to spontaneously close the perforation or the surgeon's inability to get engraftment and surgical closure. For example, traumatic perforations of the tympanic membrane generally, close spontaneously within three months of the injury. Perforations caused by hot slag burns in welders are notoriously difficult to get to heal even with surgical intervention. Blast injuries from improvised explosive devices spontaneously heal in less than 50% of cases. The latter two conditions may be due to poor vascularity of the cauterized remnant TM and damaged external auditory canal skin.

Other etiologies such as acute otitis media, poor eustachian tube function, or retained tympanostomy tubes can predispose to chronic perforations as well. Ingrowth of squamous epithelium from the outer layer of the TM around the edge into the middle ear through the perforation preventing fibroblast proliferation and contraction of this wound may prevent spontaneous healing also. While small perforations are not usually associated with hearing loss, large perforations can be associated with a significant conductive hearing loss (up to 30 dB SPL).

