3.2 Clinical Use of FGF-2

A study in 87 subjects with chronic tympanic membrane perforation was recently published. The objectives of the study was to measure the rate of complete closure of chronic TMR using basic fibroblast growth factor (bFGF) combined with an atelocollagen/silicone bilayer membrane patch. The study assessed closure of TMR in 87 subjects using bFGF, which is thought to promote the regeneration of TM tissues by facilitating the growth of fibroblasts and collagen fibers. A dose of 10 mcg of bFGF was administered every 21-days. Study methods included a procedure using an operating microscope. The results of the study reported mean perforation size before treatment of 14.4%. Complete closure of the TMR was achieved in 80 subjects (92.0%), whereas pinholes remained in 5 subjects (5.7%), and small perforations were observed in 2 subjects (2.3%). In the subjects with complete closure, the TMR closed after an average 1.8 treatments, and hearing improved by 13.6 dB. In conclusion the study demonstrated that bFGF combined with atelocollagen is effective for the conservative treatment of TMR (Hakuba et al, 2009).

Kanemaru et al (2011) have reported updated findings from their 2009 presentation involving 63 subjects, in which 53 received tympanic membrane repair using gelatin sponge and fibrin glue with b-FGF and 10 were assigned to the control group of gelatin sponge and fibrin glue alone. The study sought to determine closure rates, hearing level, and sequelae after 3 weeks post treatment. Of the 53 subjects who received b-FGF treatment, 52 had a complete closure of the TMP (98.1%) compared to 1 out of 10 (10%) of the control group subjects. Hearing level improved for all subjects with successful TM repair. No serious sequelae were observed. Some of the perforations were pan tympanic and included loss of nearly all of the tympanic membrane. They concluded that bFGF may be a simple, cost-effective treatment option for subjects with chronic tympanic membrane perforations. Human FGF-2 has been the most studied FGF isoform and its production and clinical applications in wound healing are well described.

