10.2 Method of Assigning Subjects to Treatment – Randomization

To generate the randomization scheme, a random number generator program known as Research Randomizer will be used (Urbaniak & Plous, 2013). Subjects will be randomly

assigned to unequal treatment groups in a 3:1 ratio. A random number scheme will be created containing 15 sets of numbers with 4 unique numbers per set (1-4) [total of 75 numbers corresponding to 75 subjects]. Of the 4 numbers per set, patients assigned to numbers 1, 2, or 3 will receive FGF-2 and patients assigned to number 4 will receive placebo. Once the random numbers are generated, the pharmacy will create an Excel spreadsheet with the FGF-2 and placebo assignments corresponding to the numbers that were generated.

Randomization assignments will be done centrally by the MEE pharmacy. Subjects are assigned to treatment by placing the subject's name on the next available line of the spreadsheet. For subjects treated at MEE, the pharmacist uses this information to prepare the proper treatment for the subject. For subjects at the Willford Hall location, the randomization assignment will be communicated to designated staff at Willford Hall via secure email.

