17.1 Determination of Sample Size

The target enrollment of 60 subjects will provide sufficient power while also accounting for potential retention issues. With recruitment of only 44 subjects, we will reach a power of .80. This gives room for some attrition, although we think it will not be more than 5%.

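### Section 17.5 lists Student's t-test in a 3:1 trial; naming Welch's version for hearing change is a nearly costless safeguard if the arms' spreads differ

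*Combined protocol and SAP*

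**What the plan says.** Section 17.5 (Efficacy Analysis) says that efficacy data from the randomized phase will be evaluated by inspection and "using student T-test, Cochran Mantel Hansel, or Kruskal-Wallis tests as appropriate", and adds "without conservation of alpha at 0.05". It assigns no test to any outcome, does not say whether variances are pooled, and offers no unequal-variance version. Section 17.6 covers only categorical secondary data.

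Change in pure-tone and speech discrimination scores is a secondary objective (Sections 4.2 and 5.1). Section 10.2 has subjects "assigned to unequal treatment groups in a 3:1 ratio". The Synopsis requires 45 FGF-2 and 15 placebo patients, and Section 17.1 gives a target of 60. The Synopsis elsewhere plans 75, which is about 56:19 at 3:1.

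On hearing, the Introduction (Section 2) says that "small perforations are not usually associated with hearing loss, large perforations can be associated with a significant conductive hearing loss", with a ceiling of 30 dB. Section 3.2 reports from an 87-subject study that, in subjects with complete closure, "the TMR closed after an average 1.8 treatments, and hearing improved by 13.6 dB". No SD of hearing change is given for either arm.

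**The concern.** Of the three listed tests, Cochran-Mantel-Haenszel in its usual form is for categorical data and Kruskal-Wallis works on ranks. Only Student's t compares mean change in dB, so an analyst following Section 17.5 would probably use it for hearing.

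The pooled test tolerates unequal spreads when the arms are about equal in size. At 3:1 it does not. The pooled variance is dominated by the large arm, while the true standard error is dominated by the small one.

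Unequal spread is plausible here, though not established. Subjects who close recover an amount that depends on how much hearing they had lost, and subjects who stay open recover little. If closure differs between arms, the SDs of hearing change may differ too. At stake are the standard error, p-value and any interval for two secondary comparisons.

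**Working it through.** **The plan's own figures.** The plan gives no power or precision figure for hearing change. Its power figures concern closure: "more than 90% power to detect a clinical significant difference" with 45 + 15 patients "at a two-sided significance level of 0.05" (Fisher's exact test), and "With recruitment of only 44 subjects, we will reach a power of .80" in Section 17.1. No closure rates are stated, so neither can be reproduced directly. They agree with each other: rate pairs giving 80% power at 33:11 (from 10% vs 55% up to 50% vs 92%) give 90.6–91.6% at 45:15. The pair 10% vs 55% is used below for that reason.

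**Step 1: what pooling does at 45:15.** Let s1 be the FGF-2 SD and s2 the placebo SD. Note 1/45 + 1/15 = 4/45.

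- True SE² = s1²/45 + s2²/15 = 0.0222 s1² + 0.0667 s2².
- Expected pooled SE² = [(44 s1² + 14 s2²)/58] × 4/45 = 0.0674 s1² + 0.0215 s2².

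The weights are nearly swapped. Example with s1 = 1.5 and s2 = 1: pooled √0.173 = 0.416, true √0.117 = 0.342, ratio 1.22.

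**Step 2: equal means, unequal SDs (hypothetical).** Simulation with normal data, no true difference, nominal two-sided 5%, 400,000 runs per row:

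| SD ratio FGF-2/placebo | Pooled SE / true SE | Student error | Welch error |
|---|---|---|---|
| 0.5 | 0.73 | 15.3% | 5.1% |
| 0.67 | 0.82 | 10.6% | 5.1% |
| 0.8 | 0.89 | 8.0% | 5.0% |
| 1 | 1.00 | 5.0% | 5.1% |
| 1.25 | 1.12 | 2.9% | 5.1% |
| 1.5 | 1.22 | 1.8% | 5.0% |
| 2 | 1.37 | 0.9% | 5.0% |

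At 56:19 the results are almost the same (15.1% at ratio 0.5, 0.9% at ratio 2). At 30:30 Student stays at 5.1–5.2%, so the 3:1 split is the cause.

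**Step 3: an illustrative model for hearing change.** From the documents: mean gain on closure 13.6 dB, limit 30 dB, closure 92% (87-subject study) or 98.1% with FGF-2 against 10% in controls (gelatin-sponge study), all in Sections 2 and 3.2; and 41% control closure, from the chinchilla study in Section 3.1. Assumed: SD of gain 8 dB (alternative 3 dB), gain limited to 0–30 dB, no gain without closure, retest SD 5 dB.

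For closure rate p, gain mean m, gain SD g and retest SD e: arm variance = p g² + p(1 − p) m² + e².

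- *Gain SD 8 dB, 92–98% vs 10%.* After limiting to 0–30, m is about 13.7 and g about 7.5. At 92%: 0.92 × 7.5² + 0.92 × 0.08 × 13.7² + 25 ≈ 91, SD about 9.5. At 10%: 0.10 × 7.5² + 0.10 × 0.90 × 13.7² + 25 ≈ 47.5, SD 6.9. Over 92–98% the FGF-2 SD is about 9.2–9.6. Simulated 95% half-widths are 5.2–5.3 dB (Student) and 4.5–4.6 dB (Welch), with Student coverage about 97.8%. The mean difference is 11–12 dB, so power is 99.0–99.6% (Student) against 98.7–99.4% (Welch).
- *Gain SD 8 dB, 55% vs 10%.* Half-widths are 5.6 and 4.7 dB, and power is about 60% and 72%.
- *Gain SD 3 dB, 92% vs 41%.* FGF-2: 0.92 × 9 + 0.92 × 0.08 × 13.6² + 25 = 46.9, SD 6.8. Placebo: 0.41 × 9 + 0.41 × 0.59 × 13.6² + 25 = 73.4, SD 8.6. Pooled SE = √(0.0674 × 46.9 + 0.0215 × 73.4) = 2.18; true SE = √(46.9/45 + 73.4/15) = 2.44. Student is too narrow, with coverage about 92%.
- *Near-equal spreads.* With gain SD 3 dB and 92% vs 10%, the SDs are 6.8 and 6.5. With gain SD 8 dB and 92% vs 41%, they are also nearly equal. In both cases the two tests roughly agree.

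**Step 4: the null case in the same model.** With equal closure in both arms (10%, 30%, 50% or 92%) the spreads are equal. Student's error is then about 5%, and Welch's is 5.1–5.6%.

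**The case against.** The case against making much of this is strong, and most of it stands.

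- **The plan does not commit to a t-test of hearing.** It is one of three tests to be used as appropriate, and Kruskal-Wallis is available, although that too is affected by unequal spread and gives no interval in dB. Section 13.2 also defines thresholds for a clinically significant hearing change, so hearing could be analysed as a categorical outcome. Section 17.5 plans no confidence interval.
- **Pooling is the conventional meaning of Student's test, but the text does not say so.**
- **No SDs are given.** A reader might infer that the documents imply unequal spreads and that the hearing standard errors will be wrong. They do not go that far: Step 3 shows near-equal spreads under equally reasonable assumptions.
- **A reader might infer a false-positive rate of up to 15%.** That needs equal means with unequal SDs. The only reason the documents offer for unequal spreads is unequal closure. With no effect on closure, spreads are equal and Student's error is about 5%.
- **A reader might infer a material power loss at the cited closure rates.** There is none: both tests have about 99% power at 92–98% vs 10%.
- **The stakes are limited.** Hearing is secondary, the primary comparison is binary, and the same sentence of Section 17.5 disclaims alpha control. The unassigned list of tests is the larger defect there.

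What survives is narrower. The SD ratio cannot be known in advance, nothing in the plan directs the analyst to a version that remains valid when it differs from 1, and choosing after seeing the spreads would add a data-driven step.

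**Conclusion.** A cheap improvement to the stated method, not an error that invalidates a planned result. If Student's pooled test is used for hearing change at 45:15 and the arm SDs differ, its standard error can be too large or too small. For SD ratios from 0.5 to 2 it runs from 27% too small to 37% too large.

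In the illustrative model the practical effect ranges from nothing, through half-widths about 15–20% wider than Welch's, to coverage of about 92%. A noticeable power loss (about 60% against 72%) appears at 55% vs 10% closure. All of this rests on assumed SDs of gain and retest error.

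Inflated type I error remains a hypothetical case. The conclusion barely changes between 60 and 75 subjects, and the primary closure comparison is unaffected.

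**What to change.** In Section 17.5, replace Student's t-test with: *Welch (unequal-variance) two-sample t-test, reported with its 95% confidence interval, for continuous outcomes such as change in pure-tone and speech discrimination scores.* This also ties one of the listed tests to a named outcome.

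The change takes a few words and needs no new data. If the SDs are in fact equal, Welch loses about 2 points of power at 45:15 (roughly 80% to 78%).
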